8.5.3. Survival Follow-up

Once the study is unblinded, survival follow up will continue. All subjects who are alive after an EFS event will be contacted every 8 weeks for survival follow-up until death, withdrawal by subject, loss to follow-up, or when the Sponsor ends the study.

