8.5.2. Event-Free Survival Follow-up

All subjects who discontinue study treatment without experiencing any 1 of the following: death, disease relapse, treatment failure, or withdrawal of consent, will be followed every Day 1 (± 7 days) of Weeks 9, 17, 25, 33, 41, 53, and every 24 weeks thereafter for EFS until they experience treatment failure, relapse, death, withdraw from the study, or until the time when 173 EFS events have occurred or as deemed necessary by the IDMC.

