6.3.7. Last Contact Date

The last contact date will be derived using the last complete date in the eCRF on or before the data cutoff date, from among the following:

- All assessment dates (eg, vital signs assessment, ECG assessment)
- Dates of administration of study drug, concomitant medications, and subsequent anticancer therapies
- Start and end dates of AEs
- Last contact date collected on the Survival Follow-up eCRF when the subject status is alive
- Randomization date
- Withdrawal of consent date
- Date of discontinuation on disposition eCRF pages. If the option “Lost to Follow-up” is selected, the corresponding date will not be used in the derivation of last contact date

Notes:

- Only dates associated with actual examinations of the subject will be used in the derivation. Dates associated with a technical operation unrelated to subject status, such as the date a blood sample is processed, will not be used.
- Assessment dates after the data cutoff date will not be used to derive the last contact date.

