7.7.2.2. Overall Survival

Overall survival is defined as the time from date of randomization to the date of death due to any cause. If a subject is not known to have died by the data cutoff date, then OS will be censored at the date of last contact (see [Section 6.3.7](#)).

If the primary analyses of EFS and CR rate are significant, OS will be tested using the log-rank test stratified by the randomization stratification factors at 1-sided 2.5% level of significance.

The HR will be estimated using a Cox's PH model stratified by the randomization strata. Each stratum will define a separate baseline hazard function (using the "STRATA" statement in SAS PROC PHREG), ie for the i -th stratum the hazard function is expressed as: $h(i;t)=h(i,0;t)\exp(x\beta)$, where $h(i,0;t)$ defines the baseline hazard function for the i -th stratum

and x defines the treatment arm (0=control arm, 1=treatment arm) and β is the unknown regression parameter. Ties will be handled by replacing the PH model by the discrete logistic model (Ties=Discrete option in SAS PROC PHREG).

Kaplan-Meier estimates (product-limit estimates) will be presented by treatment arm together with a summary of associated statistics including the median OS time with 2-sided 95% CIs. In particular, the OS rate at 3, 6, 9, 12, 18, 24 and 36 months will be estimated with corresponding 2-sided 95% CIs. The CIs for the median will be calculated according to Brookmeyer and Crowley and the CIs for the survival function estimates at the time points defined above will be derived using the log-log transformation (confotype=loglog default option in SAS PROC LIFETEST) with back transformation to a CI on the untransformed scale. The estimate of the SE will be computed using Greenwood's formula.

Frequency of subjects with an event (death) and censoring reasons will be presented by treatment arm. Reasons for censoring will be summarized according to the categories in Table 7 following the hierarchy shown.

Table 7: OS Censoring Reasons and Hierarchy

Hierarchy	Condition	Censoring Reason
1	No event and (EOS date \geq date of randomization when reason for EOS=Withdrawal by Subject)	Withdrawal of consent
2	No event and [(lost to follow-up in any disposition page or survival follow-up page) or (data cutoff date–last contact date >8 weeks)]	Lost to follow-up
3	No event and none of the conditions in the prior hierarchy are met	Alive

Abbreviations: OS=overall survival; EOS=end of study.

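### SAP Table 7 can report on-schedule, event-free subjects as lost to follow-up for OS, and the protocol gives them no survival-contact interval after 173 EFS events

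*Protocol*

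**What the plan says.** **Protocol, survival follow-up.** Section 8.5.3 states: "All subjects who are alive after an EFS event will be contacted every 8 weeks for survival follow-up until death". The same restriction appears in the Synopsis, in Sections 7.1, 9.11.1 and 10.1, and in footnote 25 of the Schedule of Assessments.

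**Protocol, EFS follow-up.** Under Section 8.5.2, subjects who stop treatment without an EFS event are seen at "Weeks 9, 17, 25, 33, 41, 53, and every 24 weeks thereafter for EFS". This continues until an event or withdrawal, "or until the time when 173 EFS events have occurred or as deemed necessary by the IDMC". Footnote 14 of the Schedule of Assessments stops disease evaluation once the sponsor unblinds the study.

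**Protocol, text pointing the other way.** Section 8.5.4 keeps subjects who stop treatment before progression or relapse under observation for death as well as for progression and relapse. Section 9.8.1 sends a subject who stops AG-120/placebo without an EFS event to EFS follow-up and then on to survival follow-up.

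**SAP.** Section 7.7.2.2 says that if no death is known by cutoff, "then OS will be censored at the date of last contact". Table 7 then assigns a censoring reason. A subject without an event is classed as lost to follow-up if a disposition or survival follow-up page says so, or if "data cutoff date–last contact date >8 weeks". Section 6.3.7 adds: "Assessment dates after the data cutoff date will not be used to derive the last contact date".

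**The concern.** The 8-week threshold in Table 7 matches the survival follow-up interval, but the table applies it to every subject without a death. Event-free subjects off treatment are not on that interval. After Week 41 a subject can attend every scheduled visit and still exceed 8 weeks. The same subject may then be ongoing without relapse or death in the EFS censoring table (SAP Table 6) and lost to follow-up in the OS table.

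The loss-to-follow-up count is a basic measure of trial quality and is read by arm. The plan assumes twice as many responders with AG-120, so a rule that mislabels responders would probably inflate the count more in that arm.

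The protocol also leaves it unclear how these subjects are contacted for survival once EFS follow-up closes at 173 events. OS is a key secondary endpoint with modest power, and survival follow-up is meant to continue after unblinding.

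**Working it through.** **1. The plan's own OS figure.** Inputs from Protocol 12.13.1: 145 deaths, HR 0.71, 1-sided 2.5%, 1:1 allocation. Schoenfeld's formula gives z = (√145 / 2) × |ln 0.71| − 1.960 = 6.021 × 0.3425 − 1.960 = 0.102, so power = Φ(0.102) = 54.1%. The stated 54% is reproduced.

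**2. Visit gaps against the 8-week rule.** The Section 8.5.2 schedule gives gaps of 8 weeks from Week 9 to Week 41, 53 − 41 = 12 weeks, then 24 weeks. The SAP restates this schedule in Section 7.7.1.1.1. Assume that the cutoff falls uniformly within a gap of g weeks and that no other contact is dated. The share of cutoff dates on which a compliant subject is labelled lost is max(0, (g − 8)/g).

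| Gap g (weeks) | Share labelled lost | Mean time since last visit (weeks) |
|---|---|---|
| 8 | 0% | 4 |
| 12 (Weeks 41–53) | 4/12 = 33% | 6 |
| 24 (after Week 53) | 16/24 = 67% | 12 |

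The ±7-day windows can lengthen a gap by up to 2 weeks. A 24-week gap becomes 26 weeks (18/26 = 69%). An 8-week gap becomes 10 weeks (2/10 = 20%), so the rule needs an allowance for the window even on the 8-week schedule.

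**3. How many subjects.** At 173 events at most 200 − 173 = 27 subjects (13.5%) lack an EFS event. This is a ceiling. It includes those still on treatment, who have visits every 4-week cycle, and those already censored. The documents do not give the off-treatment share.

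**4. Likely split by arm.** The expected number event-free in an arm is the sum over its subjects of CR rate × 2^(−follow-up/median). Inputs from Protocol 12.12: CR 20% vs 40%, responder medians 14.6 vs 19.2 months, and the stated accrual. Dropout is ignored.
- Around month 47: 7.7 control and 18.9 AG-120, total 26.6, of which 18.9/26.6 = 71% are in the AG-120 arm.
- At month 52, the planned analysis time: 6.1 and 15.8, total 21.9, of which 15.8/21.9 = 72% are in the AG-120 arm.

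**5. Effect on the OS test.** SAP 6.2.2 places the key secondary analyses at the EFS cutoff, so what happens after 173 events does not reach the confirmatory test. The Table 7 reason does not enter the analysis, because censoring is at last contact under either label. Deaths not yet known at cutoff are the only route to the test. If 1, 2, 5 or 10 of the 145 were missed, power would be 53.8%, 53.5%, 52.6% or 51.2%.

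**6. The protocol sections side by side.** Section 8.5.3 and its repeats give a contact interval only after an EFS event. Section 8.5.2 ends EFS visits at 173 events, and footnote 14 ends disease evaluation at unblinding. No scheduled assessment would then document the relapse that brings a subject under 8.5.3. Sections 8.5.4 and 9.8.1 say that these subjects are still followed for death and do pass to survival follow-up, but neither gives an interval.

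**The case against.** A reader might infer from 8.5.3 that event-free responders are excluded from survival follow-up. The documents do not support that. Sections 8.5.4 and 9.8.1 keep them in, and 9.11.1 also speaks of EFS/survival follow-up. Reaching 173 events while event-free is not among the reasons for leaving the study in 8.5.4. A responder who relapses during EFS follow-up then falls under the 8-weekly rule. So the protocol contradicts itself and leaves out an interval; it does not exclude these subjects.

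A reader might also infer that the OS comparison is biased. Neither document plans an OS analysis after the EFS cutoff, and the label affects one descriptive table. An unplanned later update would in any case also be affected by the permitted crossover from placebo.

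The percentages are upper bounds. SAP 6.3.7 takes last contact from all assessments, adverse event dates, medications and subsequent therapies, so some subjects will have a more recent date. A survival check before cutoff is an operational step that nothing in the plan forbids.

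All of this stands and limits the impact. It does not remove the mismatch in Table 7, which no other SAP text resolves, or supply the missing contact interval.

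**Conclusion.** The point holds as a misclassification rule in the SAP and an unresolved contradiction in the protocol.

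- **Table 7.** Fully compliant, event-free subjects off treatment can be reported as lost to follow-up for OS, on up to 33% of possible cutoff dates in the Week 41–53 gap and up to 67% after Week 53. This assumes a cutoff at random between visits and no other dated contact. It distorts the loss-to-follow-up count, probably more in the AG-120 arm given the assumed response rates.
- **Survival contact.** No section sets an interval for these subjects after 173 events. At cutoff their survival status can be about 24 weeks old (about 26 with windows), and later OS updates could lose them.
- **Size.** Those affected are a subset, of size not given in the documents, of at most 27 subjects. The confirmatory OS test at 145 deaths and 54% power is essentially unaffected.

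The consequence is modest, but the rule gives a wrong result as written and is cheap to correct.

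**What to change.** 1. **SAP Table 7.** Assign lost to follow-up from the disposition or survival follow-up record, or when time since last contact exceeds the subject's own scheduled interval plus its window.
2. **Protocol 8.5.3 and its repeats.** Reconcile them with 8.5.4 and 9.8.1. State that all off-treatment subjects who have not withdrawn are contacted for survival every 8 weeks regardless of EFS status, including after 173 EFS events.
3. **Data cutoff.** Add one survival-status check timed to the cutoff and dated on or before it, because SAP 6.3.7 does not use later assessment dates.

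The cost is wording in both documents and a small number of extra telephone contacts, for at most 27 event-free subjects once 173 events are reached. The planned OS deaths and power do not change.

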8.5.4. Withdrawal from the Study

Subjects discontinuing study treatment prior to experiencing disease progression/relapse will continue to be followed for disease progression/relapse/death. The reasons for withdrawal from the study include:

- Withdrawal by subject
- Subject lost to follow-up
- Study terminated by Sponsor
- Death

9. STUDY TREATMENT

9.1. Description of Study Drug

AG-120 will be supplied as 250 mg-strength tablets to be administered orally. Placebo will be supplied as matched tablets to be administered orally. Inactive ingredients of AG-120 tablets are hypromellose acetate succinate, microcrystalline cellulose, croscarmellose sodium, sodium lauryl sulfate, colloidal silicon dioxide, magnesium stearate, and Opadry® II Blue. The inactive ingredients of placebo to match AG-120 tablets are microcrystalline cellulose, mannitol, magnesium stearate, and Opadry® II Blue.

Azacitidine will be supplied by the Sponsor as a sterile lyophilized powder containing 100 mg azacitidine and 100 mg mannitol per vial, to be reconstituted and administered SC or IV.

AG-120 is provided for investigational use only (considered an investigational medicinal product; IMP) and is to be used only within the context of this study. Azacitidine is also considered an IMP for this Phase 3 study, with the exception of sites in Brazil, where azacitidine will be supplied as commercial product. All study drug products will be supplied by the Sponsor. Please see the respective IBs for further details regarding AG-120 and azacitidine.

9.2. Study Drug Packaging and Labeling

AG-120 and matched placebo will be supplied in appropriate containers with child-resistant closures and will be labeled appropriately as IMP for this study.

Azacitidine will be supplied in sterile single-use vials and will be labeled appropriately as IMP for this study (or for investigational use, for sites in Brazil).

Packaging and labeling will be prepared to meet all regulatory requirements.

9.3. Study Drug Storage

AG-120 tablets, matched placebo tablets, and azacitidine vials must be stored according to the respective package label.

All study drug products must be stored in a secure, limited-access location and may be dispensed only by the Investigator or by a member of the staff specifically authorized by the Investigator.

9.4. Method of Assigning Subjects to Treatment

Subjects who meet all study eligibility criteria will be randomly assigned in a 1:1 ratio to receive AG-120 500 mg orally QD plus 75 mg/m²/day SC or IV azacitidine or AG-120-matched placebo orally QD plus 75 mg/m²/day SC or IV azacitidine. Randomization will be stratified by de novo status (de novo AML and secondary AML) and geographic region (United States and Canada; Western Europe, Israel, and Australia; Japan; and rest of world).

The randomization schedule will be generated by an independent statistical group; all study site personnel (Investigators, study coordinators, study pharmacists) and the Sponsor will be blinded to study treatment. The randomization assignment will be implemented by interactive response technologies (IRT).

9.5. Blinding

The subjects, Investigators, Sponsor, and the clinical research unit staff who deal directly with subjects will all be blinded to study treatment assignment. The IRT will assign each subject specific Medication ID-labeled study drug containers and azacitidine vials. AG-120 and matched placebo will be packaged and labeled identically so that the study pharmacist will remain blinded to treatment assignment.

The subjects, Investigators, Sponsor, and the clinical research unit staff will remain blinded for the duration of the study until the final analysis for the primary endpoint unless emergency unblinding is required (see Section 9.6). An IDMC will review unblinded safety data and other clinical data, including efficacy data, at scheduled meetings; the unblinded summaries will be prepared by an independent statistical center (see Section 10.6.1).

9.6. Unblinding

The need to unblind study treatment should first be discussed with the Sponsor's Medical Monitor (or Medical Director). In the event of a medical emergency or pregnancy in a female subject, or in the female sexual partner of a male subject, in which knowledge of the investigational product is critical to the subject's management, the blind for that subject may be broken by the treating Investigator. Investigators are encouraged to discuss a plan to break the blinding code with the Medical Monitor.

In the case of an emergency, the Investigator may access the IRT to reveal the identity of the treatment for that subject. Once the decision to unblind has been made, the Investigator must record the nature of the emergency that required the unblinding, along with the date and time of the unblinding on the proper source documentation and notify the Sponsor's Medical Monitor (or Medical Director) of the unblinding.

In the event that a subject's treatment assignment is unblinded, either accidentally or in the case of emergency unblinding, the subject will be allowed to continue study treatment (if there is no disease progression).

In cases where Investigators may need to know prior study treatment assignment, (eg, an SAE is treated differently based on exposure status), an Investigator may request subject unblinding. In such situations and with Medical Monitor approval, the subject and site staff will be unblinded to a subject's treatment assignment after documented disease progression (as assessed by the Investigator and after discussion with the Sponsor's Medical Monitor).

Primary Endpoint Results and Subsequent Study Unblinding: Once the primary endpoint of EFS is statistically analyzed, the Sponsor will communicate the topline aggregate results of the study to participating site investigators and via public disclosure. Shortly after public disclosure of the topline aggregate results, the Sponsor will communicate to all sites the treatment assignments of all subjects and will also inform sites which of the 2 following scenarios to pursue following unblinding.

If the benefit-risk profile favors treatment, all ongoing subjects randomized to receive placebo + azacitidine who meet key safety eligibility criteria will be given the opportunity to receive AG-120 + azacitidine following unblinding. Subjects who were already receiving AG-120 + azacitidine may continue to receive treatment on the same assessment schedule. Prior to

crossover to AG-120, investigators will evaluate subjects for Inclusion Criteria 5 and 6 and Exclusion Criteria 8, 12, 13, and 17 to determine safety eligibility.

If the benefit-risk profile does not favor treatment, crossover will not be permitted; however, all ongoing patients will be permitted to receive their assigned study treatment at the discretion of the treating investigator.

9.7. Study Drug Preparation and Administration

Subjects may not receive study treatment for each treatment cycle until all Day 1 procedures have been completed and all doses of study treatment from the prior treatment cycle have been accounted for, including the number of missed doses (where applicable). For females of reproductive potential, a serum β -hCG pregnancy test (sensitivity of at least 25 mIU/mL) must be performed at Screening within 72 hours prior to study treatment administration and be verified as negative.

The first day of study treatment dosing is considered Day 1 of a cycle.

Subjects will be monitored for hematologic toxicity and non-hematologic (if thought to be causally related) toxicity, with the NCI CTCAE version 4.03 used as a guide for the grading of severity (see Section 11.2). Dosing interruptions or delays or dose modifications may occur for managing toxicities and/or treatment response during study treatment (see Section 9.8).

9.7.1. AG-120 and Matched Placebo

AG-120 (500 mg) or matched placebo will be administered orally QD (approximately every 24 hours) during Weeks 1 to 4 in continuous 4-week (28-day) cycles. Crossover between treatment arms will not be permitted until the study is unblinded and the primary endpoint reaches statistical significance (see Section 9.6). Subjects should be instructed to take their QD dose at approximately the same time each day. Each dose should be taken with a glass of water and consumed over as short a time as possible.

Subjects should be instructed to swallow tablets whole and not to chew the tablets. Subjects may take AG-120 or placebo tablets with or without food. Subjects should be advised that if AG-120/placebo tablets are taken with food, the subject should avoid grapefruit or grapefruit products and avoid consuming a high-fat meal (refer to representative examples of low-fat and high-fat, high-calorie meals in Appendix 15.1).

If the subject forgets to take the daily dose, they should take AG-120 or placebo within 12 hours after the missed dose. If more than 12 hours have elapsed or if the dose was vomited, that dose should be omitted and the subject should resume treatment with the next scheduled dose.

Subjects will be dispensed the appropriate number of Sponsor-packaged, labeled bottles to allow for dosing for a full cycle; alternatively, they may be dispensed appropriate bottle(s) until the next scheduled visit. Subjects are to return all unused tablets (or the empty bottles) on Day 1 (\pm 3 days) of each treatment cycle or at the next scheduled visit.

Subjects will be given a dosing diary for each treatment cycle. They should record relevant information regarding their study drug in the diary (eg, confirmation that each daily dose was taken, reasons for missed doses).

Treatment compliance (see Section 9.11.3) will be assessed based on the return of unused drug and the dosing diary (see Section 9.12 and Section 9.13).

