9.10. Other Potential Risks

9.10.1. Leukoencephalopathy

Leukoencephalopathy is a potential risk associated with AG-120 treatment based on clinical safety findings observed across the AG-120 clinical development program. Progressive multifocal leukoencephalopathy and posterior reversible encephalopathy syndrome (PRES), both Grade 3 SAEs, have each been reported in 1 subject.

The signs and/or symptoms of PML may begin gradually, usually worsen rapidly, and vary depending on which part of the brain is infected. Signs and symptoms may include difficulty with walking and other movements, progressive weakness, decline in mental function, visual field deficits, and speech and language disturbances. Rarely, headaches and seizures occur. Subjects should be monitored for onset of signs or symptoms suggestive of PML. Diagnostic evaluations may include consultation with a neurologist, magnetic resonance imaging (MRI) of the brain, lumbar puncture, and/or brain biopsy as clinically warranted. The Investigator should immediately contact the Study Medical Monitor when PML is a suspected or confirmed diagnosis. Treatment with AG-120/placebo should be suspended in the setting of suspected PML and permanently discontinued in subjects with confirmed PML. Subjects with a prior history of PML should not be treated with AG-120 and are excluded from this study.

Posterior reversible encephalopathy syndrome is a rare clinic-radiological neurological syndrome ([Linda and von Heijne, 2015](#)). Clinical characteristics may include subacute onset of headache, hypertension, seizures, altered mental status, visual disturbances, and occasionally other focal neurological signs. Radiologically, signs of vasogenic edema are usually seen bilaterally in the white matter of the parieto-occipital lobes, but changes can also be seen in frontal and temporal lobes, brainstem, cerebellum, and in cortical as well as deep gray matter. Subjects should be monitored for onset of neurological signs and/or symptoms that are clinically associated with PRES. Diagnostic evaluations may include consultation with a neurologist, MRI of the brain, and other recognized standard of care measures as clinically warranted. Additionally, the Investigator should consult with the Study Medical Monitor for management guidelines to be utilized in the setting of suspected or confirmed PRES.

Refer to the AG-120 IB for further details on these events.

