9.11.2. End of Study

At the time of primary endpoint analysis (approximately 173 EFS events or as deemed necessary by the IDMC), the study will be unblinded. Subjects on treatment at that time may continue receiving study drug. After unblinding, and if the benefit-risk profile favors treatment, subjects randomized to placebo may be offered the choice to receive AG-120. End of Study is defined as the time at which all subjects have died, discontinued the study, are lost to follow-up, or have withdrawn consent; or when the Sponsor ends the study.

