6. GENERAL STATISTICAL CONSIDERATIONS

6.1. Randomization, Blinding, Unblinding, and Crossover

Subjects will be randomized in a 1:1 ratio to one of the following treatment arms:

- AG-120+azacitidine=AG-120 500 mg QD orally plus azacitidine 75 mg/m²/day SC or IV
- Placebo+azacitidine=AG-120-matched placebo QD orally plus azacitidine 75 mg/m²/day SC or IV

Randomization assignment will be implemented by interactive response technology (IRT) and stratified by:

- AML status (de novo AML; secondary AML)
- Geographic region (United States and Canada; Western Europe, Israel, and Australia; Japan; ROW)

This is a double-blind study therefore the subjects, Investigators, Sponsor, and the clinical research unit staff who work directly with subjects will all be blinded to study treatment assignment.

At the time of the DBL for the final analysis of the primary endpoint, the study will be unblinded. Subjects on treatment at that time may continue receiving study treatment.

After unblinding, and if the benefit-risk profile favors AG-120+azacitidine, subjects randomized to placebo+azacitidine may be offered the choice to receive AG-120.

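### Section 9.7.1 makes crossover depend on a significant primary endpoint, Section 9.6 on benefit-risk alone; the crossover safety list also leaves out the PML exclusion

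*Protocol*

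**What the plan says.** **Opening crossover.** Protocol Section 9.7.1 (drug administration) states a bar: "Crossover between treatment arms will not be permitted until the study is unblinded and the primary endpoint reaches statistical significance (see Section 9.6").

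Section 9.6 describes what follows the primary analysis. The Sponsor tells all sites which of two scenarios applies, and the scenarios are separated by benefit-risk only. In the first, "If the benefit-risk profile favors treatment, all ongoing subjects randomized to receive placebo + azacitidine who meet key safety eligibility criteria will be given" the chance to receive AG-120. In the second, "If the benefit-risk profile does not favor treatment, crossover will not be permitted". The Synopsis repeats both scenarios under Methodology.

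Three other places mention benefit-risk only, in permissive wording. Section 9.11.2 reads "After unblinding, and if the benefit-risk profile favors treatment, subjects randomized to placebo may be offered the choice to receive AG-120"; the End of Study text in the Synopsis is similar; SAP Section 6.1 reads "After unblinding, and if the benefit-risk profile favors AG-120+azacitidine, subjects randomized to placebo+azacitidine may be offered the choice to receive AG-120".

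**Subject-level safety check.** Before "crossover to AG-120, investigators will evaluate subjects for Inclusion Criteria 5 and 6 and Exclusion Criteria 8, 12, 13, and 17". The Synopsis gives the same list. Exclusion 21, a known history of PML, is not on it. Section 9.10.1 states: "Subjects with a prior history of PML should not be treated with AG-120 and are excluded from this study".

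**The concern.** Section 9.7.1 relies on Section 9.6 for a condition that Section 9.6 does not contain. If the primary analysis misses significance but the Sponsor considers benefit-risk favorable, one section forbids giving AG-120 to placebo subjects and the other says eligible subjects will be offered it. The choice covers every placebo subject still ongoing. It also determines how much of the later survival follow-up in the placebo arm is mixed with AG-120 exposure. Left open, it would be made after the results are known.

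The safety list is a smaller matter. It is the stated gate for crossover, and a subject could pass every item on it while Section 9.10.1 says that subject should not receive the drug.

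**Working it through.** **1. The trial-level conditions side by side**

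| Place | Condition | Force |
|---|---|---|
| Protocol 9.7.1 | Unblinding and a significant primary endpoint | Barred until both hold |
| Protocol 9.6; Synopsis, Methodology | Favorable benefit-risk | Eligible subjects will be offered AG-120 |
| Protocol 9.6; Synopsis, Methodology | Unfavorable benefit-risk | Barred |
| Protocol 9.11.2; Synopsis, End of Study; SAP 6.1 | Favorable benefit-risk | May be offered |

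**2. The four possible outcomes**

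- EFS significant, benefit-risk favorable: the Section 9.7.1 bar lifts and Section 9.6 offers crossover. No conflict.
- EFS significant, benefit-risk unfavorable: Section 9.7.1 only lifts its bar and grants nothing; Section 9.6 forbids crossover. No conflict.
- EFS not significant, benefit-risk unfavorable: both forbid. No conflict.
- EFS not significant, benefit-risk favorable: Section 9.7.1 forbids and Section 9.6 offers. **Conflict.**

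The fourth outcome can be reached. Section 9.11.2 ties unblinding to the primary analysis whatever its result, and allows that analysis to be triggered by the IDMC. No section defines a favorable benefit-risk profile or links it to the EFS p-value.

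**3. What significance means here.** Section 12.5.1 gives 1-sided p ≤ 0.025, with an observed EFS hazard ratio of 0.742 or less at 173 events. With 1:1 allocation the boundary is exp(−1.96 × 2/√173) = exp(−3.92/13.153) = exp(−0.298) = 0.742. The plan's figure reproduces.

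**4. Size**

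- P(conflict) = P(EFS not significant) × P(judged favorable, given not significant).
- First factor, from the stated power in Section 12.12: 1 − 0.80 = 0.20. A rough unstratified simulation (CR 20% vs 40%, responder medians 14.6 vs 19.2 months, 200 subjects, cutoff at 173 events, 4,000 runs) gave power 0.824, hence 1 − 0.824 = 0.176.
- Second factor: not in the documents. Letting it run from 0 to 1, P(conflict) runs from 0 to about 0.20 (0 to about 0.18 on the simulation).

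**5. Effect on the formal tests.** Section 12.13.1 and SAP Section 6.2.2 place the OS test at the final EFS analysis. Crossover starts after unblinding, so neither test includes crossover exposure. In the conflict case EFS has failed, and the fixed sequence in Section 12.5 then permits no formal test of OS.

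**6. The safety list**

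- The list is Inclusion 5 and 6 and Exclusion 8, 12, 13 and 17. Exclusion 21 is absent.
- Subjects screened under Exclusion 21 were checked for PML history at entry. Appendix 15.11 shows that it entered the global protocol in Amendment 5 (09 January 2020), and the German version in May 2019. Subjects randomized earlier were not screened against it.
- PML can also arise on study. Section 9.10.1 then stops AG-120/placebo permanently. Section 9.8.1 allows azacitidine to continue, and Section 9.11.1 requires Medical Monitor approval for that. Whether such a subject counts as ongoing under Section 9.6 is not defined.

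**The case against.** The strongest reply is that the conditions are cumulative: Section 9.7.1 states a necessary condition, and the other sections add to it. For Section 9.11.2, the End of Study text in the Synopsis and SAP Section 6.1 this stands, because wording that something may be offered is compatible with a further requirement. SAP Section 6.1 is also weak evidence on its own: the SAP was written for protocol Version 7.0, before Amendment 8 added the management of subjects after unblinding. The reply does not work for Section 9.6 and the matching Synopsis text, which say that eligible subjects will be offered the drug.

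A reader might infer that sites would follow different rules depending on the section they consult. The documents do not support that. Section 9.6 has the Sponsor tell all sites which scenario to follow, so the ambiguity lies in the Sponsor's decision rule.

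A reader might also take 20% as the chance of a conflict. It is the chance that EFS misses significance. Because Section 12.5.1 makes EFS significance the basis for an efficacy claim, a favorable judgment after a miss may well be uncommon.

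On the safety list, it is fair to say that Section 9.10.1 stays in force, that Section 9.6 calls the listed items key criteria without saying they override other sections, and that suspected or confirmed PML must be reported to the Medical Monitor at once. Section 9.8.1 also sends a subject who stops AG-120/placebo through the EOT visit into follow-up, and Table 6, footnote 2 bases crossover eligibility on EOT procedures. All of this narrows the gap. What stands is that the list and Section 9.10.1 do not match.

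**Conclusion.** The inconsistency is real and limited. Section 9.7.1 conflicts with Section 9.6 and the matching Synopsis text when EFS is not significant and benefit-risk is judged favorable. The ceiling of about 20% assumes that the design assumptions hold and that the analysis takes place at 173 events. A smaller true effect, or an earlier IDMC-triggered analysis, would make a miss more likely. The probability cannot be narrowed further without a benefit-risk criterion.

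It would be wrong to conclude that the confirmatory results are at risk. The EFS test, and the OS test at the same analysis, come before any crossover. What changes is who may receive AG-120 after unblinding and how later survival data can be read.

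The missing Exclusion 21 is a narrow omission. It concerns subjects randomized before the criterion was added and subjects with on-study PML who remain on azacitidine. Section 9.10.1 reports one PML case across the development program. A reader might extend the point to Guillain-Barre syndrome, but there is no eligibility criterion for it, so the list omits nothing there. Section 9.10.2 requires permanent discontinuation of AG-120/placebo on a confirmed diagnosis; the documents do not say how such a discontinuation bears on later crossover.

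**What to change.** Reconcile Protocol Sections 9.6, 9.7.1 and 9.11.2, both Synopsis passages and SAP Section 6.1, so that one condition for opening crossover is stated throughout. Do this before the primary results are known. If benefit-risk is part of the condition, say how it relates to the EFS result.

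Reconcile the crossover list in Section 9.6 and the Synopsis with Exclusion 21 and Section 9.10.1. State what counts as an ongoing subject, and how the list relates to an earlier permanent discontinuation of AG-120/placebo, including under Section 9.10.2. Which condition and which criteria apply is a clinical decision for the Sponsor.

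The cost is a few sentences in the next protocol amendment and a matching line in the SAP. The reconciliation itself calls for no change to alpha, power, sample size or the primary analysis.
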